1 STUDY SUMMARY

Title	A Phase II Pilot Trial of Hydroxychloroquine, Everolimus or the Combination for Prevention of Recurrent Breast Cancer
Short Title	CLEVER Pilot Trial
Protocol Number	IRB #826253; UPCC 24116
Methodology	
This is a randomized, controlled, open label pilot trial. A total of 60 patients will be enrolled, with 15 patients allocated to each treatment arm. Patients will be evaluated at the initiation of every cycle for adverse events, and dose reduction will be employed for toxicity. Bone marrow aspiration will be performed at the end of cycle 3, cycle 6, and if patient continued on second treatment phase, at the end of cycle 12. The initial six-month study period is designed to assess the effects of HCQ, EVE and their combination. After three months of observation, control patients will be offered HCQ/EVE investigational therapy for six cycles; thus, the control group is actually a delayed treatment group and all patients will receive treatment. Patients who continue to demonstrate positive bone marrow DTCs after six cycles will be offered the opportunity to continue on combination therapy for an additional 6 cycles. Patients will continue to be followed for recurrence events for up to 3 years after completion of treatment.

Study Duration	Active Enrollment: 3 years; Follow-up: 3 years
Study Center(s)	The University of Pennsylvania and affiliated sites
Objectives	
Primary Clinical Objective: To evaluate the feasibility of administering HCQ, EVE or the combination in patients who have completed primary therapy for breast cancer and harbor bone marrow disseminated tumor cells
 
Endpoint: $\geq 75\%$ of patients in each arm reaching the 6-month evaluation time point without grade 3 or 4 toxicity.
 
Secondary Clinical Objectives:
 
1. To determine the safety of administering HCQ + EVE in combination with adjuvant endocrine therapy
 
Endpoints Incidence of adverse events within each treatment stratum and dose level by NCI CTCAE v4 criteria.
 
2. To evaluate preliminary efficacy of HCQ, EVE or the combination in reducing or eliminating DTCs
 
Endpoint

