7 TREATMENT PLAN

This is a randomized, controlled, open label pilot trial. A total of 60 patients

will be enrolled, with at least 15 patients allocated to each treatment group (Arms C and D constituting the same treatment group). The initial treatment period is 6 months (24 weeks). During the initial treatment period, patients will be randomized to one of 4 arms: HCQ alone (Arm A), EVE alone (Arm B), combination HCQ and EVE (Arm C) – Arm C is closing to accrual with Amendment 7 – or control/delayed combination HCQ and EVE (Arm D). Starting with Amendment 7, patients who would have been allocated to Arm C will be redirected to Arm D in order to increase the number of patients with repeat DTC assessments to aid assay reproducibility analysis. At the conclusion of 3 cycles of therapy (Arms A, B, and C) or 3 cycles of observation (Arm D), patients will undergo repeat bone marrow aspirate. Patients on Arm D will then commence combination therapy with HCQ + EVE for 6 cycles (24 weeks). After 3 cycles of therapy, patients on Arm D will undergo another bone marrow aspirate. After 6 cycles of therapy, patients on all arms will undergo another bone marrow aspirate. Patients with a negative bone marrow aspirate for DTCs at after cycle 6 will have all therapy discontinued and enter the follow up phase. Patients who have persistently positive bone marrow DTCs will be continued on combination HCQ + EVE for an additional 6 cycles (24 weeks). At the conclusion of this combination treatment period (cycle 12), all treatment will be discontinued and a bone marrow aspirate will be performed.

Patients will be evaluated at the initiation of every cycle for adverse events, and dose reductions will be employed for toxicity. Patients will continue to be followed for recurrence events for 3 years after completion of treatment.

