12.2.2 Secondary Endpoints

The secondary endpoints are tolerability/toxicity and the measured effect of the investigational therapy on DTCs in patients with measureable DTCs at baseline and the comparison of this effect to that in a control population. Because this is proof-of-concept, sample sizes are not sufficient to address long-term recurrence risk. Randomization is being performed to minimize uncontrolled confounding.

We will define “response” for each patient as a 50% or greater decrease in DTC number at each treatment time point compared to baseline. A treatment arm will be considered successful if at least 3 of 15 patients experience this predefined response endpoint. This strategy is being used to provide preliminary estimates of effect on DTCs and to assess whether one or more treatment approaches has sufficient activity to be considered in a larger study powered for relapse-free survival. We anticipate that the baseline variability in DTC measurement will lead to no more than a 4% response rate in the absence of treatment (null rate). While the trial is powered for feasibility, 15 patients provide approximately 80% power to detect a response rate of 20%, warranting further study of the treatment strategy evaluated in this patient population and clinical setting.

We will also estimate, within each treatment group, the % change in BM-DTC number, defined as the difference between BM-DTCs enumerated at 6 months and at baseline, divided by the number at baseline; we will compare this quantity across treatment groups using simple regression analyses with indicator variables for the three active treatments compared to the delayed treatment. While the trial is powered for feasibility, rather than detection of change in BM-DTCs across treatment group, 15 patients per group will provide 80% power (using a two-group t-test with a two-sided alpha level of 0.05) to detect a decrease in BM-DTCs of approximately 1 standard deviation between any two groups and will provide important preliminary data for designing future trials.

Because of tumor heterogeneity, the natural history of recurrence varies substantially between breast cancer subtypes. We have elected not to expand the

sample size to evaluate subtypes individually in this feasibility pilot, but expect that we will enroll a mix of patients across subtypes that will shed light on variability in DTCs by subtype in an exploratory fashion.

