#### Bayesian Poisson regression model

The number of DTCs observed by visit for each patient was analyzed with a Bayesian Poisson regression model that included treatment-by-visit effects and patient-level random intercepts to account for overdispersion in the outcomes. We denote observations within index  $i \in 1, ..., N$  and patients with index  $s[i] \in 1, ..., S$ . Let  $y_i$  represent the number of DTCs for observation i. The Bayesian model is specified as follows:

$$y_i \sim Pois(\lambda_i)$$
  
 $\log(\lambda_i) = \alpha + \mu_{s[i]} + X'_i \beta$ 

where  $\alpha$  is an overall intercept,  $\mu_{s[i]}$  is a patient-level intercept,  $X_i$  is a vector of treatment by visit effects, and  $\beta$  is a vector of treatment effects by visit. The following non-informative prior distributions are specified on the unknown model parameters:

$$\alpha \sim N(0, 10^2)$$
  
 $\beta_j \sim N(0, 10^2), j = 1:j$   
 $\mu_s \sim N(0, \sigma^2), s = 1:S$   
 $\sigma \sim t_3^+(0, 1)$ 

Posterior sampling was done using the *brms* package (version 2.19.0) in the R programming language (version 4.3.1). Treatment effects for HCQ, EVE, and HCQ + EVE are presented by visit as the percent reduction in mean DTCs compared to observation alone at C3. Combination effects are evaluated by comparing the mean number of DTCs with HCQ + EVE to HCQ and EVE alone by visit. The estimated probability of DTC clearance is presented by visit and treatment group. Summaries of model parameters include the posterior mean, median, standard deviation (SD), and 95% credible interval (CrI).

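### The DTC power statement and the analysis models were not updated when Amendment 7 closed Arm C and moved its patients to Arm D

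*Protocol*

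**What the plan says.** Protocol section 7 states that from Amendment 7 "patients who would have been allocated to Arm C will be redirected to Arm D", and 7.1 repeats the closure of Arm C. Section 7 also describes enrolment "with at least 15 patients allocated to each treatment group (Arms C and D constituting the same treatment group".

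Other sections keep the four-arm layout. The Study Summary says "A total of 60 patients will be enrolled, with 15 patients allocated to each treatment arm". Section 12.2.2 says "15 patients per group will provide 80% power (using a two-group t-test with a two-sided alpha level of 0.05", and that this power is "to detect a decrease in BM-DTCs of approximately 1 standard deviation between any two groups"; the Summary gives the same power for groups of 15. Section 12.2.2 prefaces the claim with "While the trial is powered for feasibility, rather than detection of change in BM-DTCs across treatment group".

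The 12.2.2 regression of percent change in DTCs has one indicator for each of three active treatments, with the delayed arm as reference. Section 12.2.1 permits, but does not require, combining C and D, and only for feasibility.

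The SAP model has treatment-by-visit effects and patient random intercepts. Effects for HCQ, EVE and HCQ + EVE "are presented by visit as the percent reduction in mean DTCs compared to observation alone at C3", and the combination is compared with each single agent by visit. Neither model has a term for enrolment period.

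**The concern.** Two things follow if the DTC analysis is run as 12.2.2 is written.

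First, the power sentence covers every pair of groups at 15 each. An Arm C that closes early cannot supply 15, so the sentence no longer describes contrasts with that arm, the only one randomised to immediate combination.

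Second, the allocation changed part-way through. If it was equal at the start (the ratio is not stated), A:B:C:D moved from 1:1:1:1 to 1:1:0:2. All Arm C patients were then randomised before the change, and Arm D, the sole source of observation data, is weighted towards the period after it. Section 12.2.2 relies on randomisation to limit confounding. That protection holds within each period, but not for a crude comparison across periods with different allocation. A change over time in assay reading or response could pass into the estimated effects, which 12.2.2 intends as input to the design of later trials.

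**Working it through.** **Inputs.** Two-group t-test, two-sided alpha 0.05, 15 per group, difference of about 1 SD (Protocol 12.2.2); 60 patients (Summary and section 7); closure of Arm C and redirection to D (sections 7 and 7.1). Assumptions: equal allocation before the amendment; A = B = 15 at the end; Arm C closes with c patients; D = 30 - c. Redirection suggests c below 15, but no document gives c, so it is treated as a range.

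**Formula.** Power is the probability that a noncentral t variable with n1 + n2 - 2 degrees of freedom and noncentrality d / sqrt(1/n1 + 1/n2) exceeds the two-sided 5% critical value.

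**The plan's own figure.** 15 v 15, d = 1: noncentrality 1 / sqrt(2/15) = 2.739, power 0.753. Power reaches 0.80 at 1.06 SD, and the normal approximation at 1 SD gives 0.78. The claim was therefore a fair rounding for 15 v 15, and 0.75 is the right reference for what follows.

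**Separate arms after the amendment.** Power at 1 SD, with the difference in SD detectable at 80% power in brackets:

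| c | D | C v A or B | C v D | A or B v D |
|---|---|---|---|---|
| 5 | 25 | 0.45 (1.53) | 0.50 (1.42) | 0.85 (0.94) |
| 7 | 23 | 0.55 (1.35) | 0.61 (1.25) | 0.83 (0.96) |
| 10 | 20 | 0.65 (1.19) | 0.70 (1.12) | 0.81 (0.99) |
| 12 | 18 | 0.70 (1.13) | 0.74 (1.08) | 0.79 (1.01) |
| 14 | 16 | 0.74 (1.08) | 0.75 (1.06) | 0.77 (1.04) |

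Example: 10 v 15 has noncentrality 1 / sqrt(1/10 + 1/15) = 2.449 and power 0.650.

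**C and D pooled.** 30 v 15: noncentrality 1 / sqrt(1/30 + 1/15) = 3.162, power 0.87, detectable difference 0.91 SD.

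**Share enrolled after the amendment.** A or B: (15 - c)/15. D: (30 - 2c)/(30 - c). Arm C: 0. Pooled C+D: (30 - 2c)/30 = (15 - c)/15, the same as A or B for every c.

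| c | C | A, B, and pooled C+D | D |
|---|---|---|---|
| 5 | 0% | 67% | 80% |
| 7 | 0% | 53% | 70% |
| 10 | 0% | 33% | 50% |
| 12 | 0% | 20% | 33% |

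Pooled combination against a single agent is thus balanced over time. Contrasts with observation are not, and contrasts with Arm C alone are furthest from balance.

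**Illustration of drift.** Take c = 10 and no treatment effect, and assume counts 1.5 times higher in patients enrolled after the amendment. This factor is an assumption; the documents report no drift. Crude means relative to the earlier period:

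- Observation (D): (10 + 10 x 1.5)/20 = 1.25
- A or B: (10 + 5 x 1.5)/15 = 1.167
- Pooled C+D: (20 + 10 x 1.5)/30 = 1.167
- Arm C alone: 1.00

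The apparent reduction against observation is 1 - 1.167/1.25, about 7%, for A, B or pooled combination, and 1 - 1.00/1.25 = 20% for Arm C alone. Pooled combination against A or B gives 0%.

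**What the planned outcomes remove.** If the factor k applies equally to a patient's baseline B and follow-up F, percent change is (kF - kB)/(kB) = (F - B)/B, so k cancels in the 12.2.2 outcome. The SAP's patient intercepts can absorb part of such a shift. Neither removes a drift between baseline and follow-up, or a change in response over time.

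**The case against.** The strongest reply is that section 7 has already redefined the groups. It counts C and D as one treatment group and asks for at least 15 in each of A, B and C+D. The SAP labels its contrasts by treatment received, not by arm. On that reading no Arm C contrast exists, combination against single agent has 0.87 power, and its allocation stays 2:1:1 throughout. The power sentence also concerns a secondary endpoint for which the protocol disclaims power, and no decision rule uses the t-test.

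Much of this stands. What remains is that 12.2.2 contradicts the grouping by keeping three active indicators against the delayed arm, that pooling is written down only for feasibility, and that the SAP's pooling has to be inferred from its labels. Pooling also does not balance the contrasts with observation, which only Arm D supplies and which the SAP presents for every treatment.

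A reader might go further and infer that Arm C contrasts are certainly underpowered and confounded with calendar time, with a false effect of 20%. The documents do not support that. The power loss depends on c, which is not given, and is negligible at c = 14. Arm C has concurrently randomised patients in A, B and D, so its comparisons are only partly non-concurrent. The 20% needs an assumed drift, raw counts and an unpooled Arm C all at once.

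**Conclusion.** The point holds as an unrevised power statement and a missing period adjustment. For Arm C alone, power at 1 SD falls from 0.75 by less than 2 points (c = 14) to about 30 points (c = 5) against A or B, and by almost nothing to about 25 points against D. A or B against D gains, to between 0.77 and 0.85. These figures assume 60 patients, A = B = 15 and D = 30 - c.

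Contrasts with observation, and any contrast with Arm C alone, are open to bias if assay reading or response drifts over time. The size is unknown; about 7% for A, B or pooled combination is an illustration, not an estimate. That part rests on equal allocation before the amendment. Because this is a secondary endpoint of a pilot, the consequence is for interpreting the DTC estimates and carrying them into later trials. The primary feasibility conclusion is not affected.

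**What to change.** 1. State Arm C's size at closure, and restate the power in 12.2.2 and the Summary contrast by contrast for A, B, pooled C+D and observation. Pooled combination and observation share the Arm D patients, so that contrast needs a calculation that allows for repeated records, not a two-group t-test.
2. State in 12.2.2 and the SAP that C and D are pooled for on-treatment DTC contrasts, in line with section 7, and say which Arm D samples count as observation and which as treatment.
3. Add an indicator for randomisation before or after Amendment 7 to the 12.2.2 regression and the SAP model. In the SAP model this adjusts for a shift in level; a drift between a patient's own visits would need the indicator by visit, as a sensitivity analysis.
4. If Arm C alone is compared with observation, repeat that comparison in concurrently randomised patients only. Under the assumptions above this is c against c, so it will be imprecise.

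The cost is restated figures, slightly less favourable for some contrasts, and one model parameter in the main analysis. No new data are needed.

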12.2.3 Translational Endpoints

We expect these studies to inform whether gene expression features, mutations, or copy number alterations predict response of DTC numbers to treatment with HCQ, GED or their combination, including alterations in the PI3K/mTOR pathway. In addition, we anticipate that these studies will identify markers in residual tumors that could serve as therapeutic targets for future trials. In addition, all analyses involving DTC counts determined by DTC-IHC will be repeated using DTC counts from DTC-Flow and results compared between the two assays.

13 CORRELATIVE SCIENCES

Patients enrolled on the CLEVER Trial will have bone marrow aspirates and blood collected serially to perform correlative studies of DTCs, CTCs and ptDNA as per the study calendar. Tumor tissue from the primary tumor (or from residual disease after neoadjuvant therapy, if applicable) will also be obtained and subjected to whole exome sequencing (WES) to obtain mutational profiles and driver mutations to be used for ptDNA biomarkers.

13.1 Biospecimens

13.1.1 Blood samples

Blood collections will be performed at the time points depicted in the study calendar, including at the time of bone marrow aspirates and then at 6-month intervals during the follow up phase for subjects who return to Penn for their follow up visits.

13.1.2 Tissue Samples

Serial sections of FFPE-fixed primary tumors will be obtained. Samples from other institutions will be shipped to our main site. A representative top section will be H&E stained by a pathologist ([name]) to identify regions of tumor and estimate tumor cellularity. Ten unstained sections of 10um thickness will be used as starting material for simultaneous extraction of DNA and RNA. Samples with cellularity lower than 25% will undergo macro-dissection to remove non-tumor tissue prior to extraction of nucleic acid. Following deparaffinization in xylene, nucleic acids will be extracted using the AllPrep DNA/RNA FFPE kit. To assess germline variation in these patients, which is required for interpretation of NGS analyses, DNA will be extracted from buffy coat samples using Genra Puregene Blood Kit. Nucleic acid concentrations and yield will be determined using a Qubit

fluorometer, A260/A280 ratios will be assessed using a NanoDrop spectrophotometer, and fragment length distribution and RNA Integrity Numbers (RIN) will be determined using an Agilent Bioanalyzer.

13.1.3 Bone marrow aspirates

Bone marrow aspirates will be obtained clinically within the outpatient setting, by qualified personnel. Only liquid aspirate will be collected, bone marrow core biopsies are not needed. The clinician obtaining the bone marrow sample will assess the anatomic landmarks before the area is prepped and draped in sterile fashion. The patient will be turned to a decubitus position and local anesthetic will be administered to the posterior iliac crest. Using a Jamshedi needle, approximately 10 ml of bone marrow fluid will be aspirated into two EDTA-containing tubes. 5 ml will be used for the standard immunohistochemical (IHC) assay which will be performed in the setting of the Pathology Department of the University of Pennsylvania. Additional 5 ml will be sent to the research laboratory of [name] at the University of Pennsylvania for DTC-FLOW analysis. Bone marrow aspirates will be divided into equal aliquots that will be used to enumerate DTCs using either DTC-Flow or DTC-IHC, and for downstream analysis. Samples will be stored at room temperature and run within 24-48 hours of aspiration.

13.2 Laboratory Assays

13.2.1 DTC Assessment by Immunohistochemistry

The presence of DTCs in the marrow by IHC is an integral biomarker required on this study for eligibility. In addition, this assay will be used to quantitate DTC response to therapy. The gold standard method for DTC assessment is immunohistochemistry (IHC), and all samples obtained during this trial will be subjected to IHC assessment. IHC to detect DTCs will be performed using the method adapted from Janni⁴ and Naume¹⁴. This well-established assay, which has been used both in prior prognostic studies and to determine trial eligibility for additional adjuvant chemotherapy¹⁴, has been replicated within the Research Pathology Laboratory of the University of Pennsylvania under the direction of [name], a co-investigator on this proposal, and subsequently implemented in our CLIA laboratory for clinical use. Briefly, 5 ml of a bone marrow aspirate sample drawn from the iliac crest under anesthesia and collected in an anti-coagulated tube containing EDTA will be stored at room temperature and processed within 24 hours. Density centrifugation using Lymphoprep will be performed and mononuclear cells (MNCs) will be harvested, washed and resuspended to 2.5×10^6 cells/ml. Cytospin slides will then be prepared from the cell suspension using a cytocentrifuge and slides will be fixed in 95% alcohol before immunostaining on a Leica Bond III autostainer. An anti-pancytokeratin monoclonal antibody will be used to screen for the presence of DTCs in the bone marrow aspirate sample. Cytospin slide containing only Hs578T cancer cell line will be used as a negative control, and a positive control containing pure MCF7 cancer cell line will be included in each run together with an antibody isotype negative control. Each cytospin will be prepared with 1×10^6 MNCs and a total of 5×10^6 cells will be evaluated per patient. Cytospin slides will be reviewed by [name] and [name] and reported. The presence

of one or more pancytokeratin positive cells with appropriate morphology of a tumor cell will be reported as positive according to the Consensus Committee morphological criteria published by Fehm⁸ and the Naume trial¹⁴. Additional cytospin slides will be prepared and stained in cases displaying atypical or indeterminate morphology.

13.2.2 Primary Tumor Analyses

RNA-seq, WES and copy number analysis (CNV) will be performed on all residual tumor specimens passing QC metrics. WES and CNV will be performed on DNA isolated from buffy coat samples.

RNA-seq: Libraries will be constructed using TrueSeq Stranded Total RNA Sample Prep followed by ribosomal RNA depletion using RiboZero (Gold). Libraries will be sequenced on the HiSeq4000 with 100 bp paired-end reads (100PE) for a total of 50M reads after the removal of low-quality reads. Quality of raw data will be confirmed by FASTQC. Reads will be aligned to the latest version of the human reference genome (hg38) with STAR¹⁰⁹ and quantified using featureCounts. DESeq2^{110,111} will be used for subsequent normalization and differential gene expression analysis.

WES: Libraries will be constructed using SureSelect v5 Library Preparation Kit. Libraries will be sequenced on the HiSeq4000 with 150 bp paired-end reads (150PE) for a total of 100M reads after the removal of low-quality reads. Quality of raw data will be confirmed by FASTQC. Reads will be aligned to the latest version of the human reference genome (hg38) with BWA-MEM¹¹². SNVs and Indels will be called using both MuTect2¹¹³ and VarScan2¹¹⁴ using tumor-normal pairs as input. Cross-comparison of calls between the tools will be used to collapse variants and reduce false-positives from germline variation.

CNV: DNA from residual lesions will be submitted for array genomic competitive hybridization (aCGH) using the Agilent SurePrint G3 4x180k array using corresponding germline DNA as reference. Quality of the array data will be assessed based on the standard QC metrics from Agilent's Feature Extraction software. Raw log ratios of copy numbers between matching tumor and buffy coat samples will be segmented using Circular Binary Segmentation in the ADaCGH2 Bioconductor package,¹¹⁵ followed by the mergeLevels postprocessing step in the same package. Copy number gains and losses will be called by fixed thresholds determined based on the distribution of the segmented and merged copy number data.

